5. TREATMENT PLAN

This is a phase II trial of atezolizumab (MPDL3280A) plus recombinant human IL-7 (CYT107) in patients with locally advanced or metastatic urothelial carcinoma. The trial follows a randomized, controlled trial design, with an initial 'Safety Run-In' phase designed to evaluate the acute safety profile of the investigational treatment combination.

During the Safety Run-In phase, 6 patients will be assigned to the experimental arm (atezolizumab + CYT107) with staggered enrollment. This will be accomplished with an initial 3 patient enrollment. All adverse events will be assessed by the Toxicity Evaluation Committee. If 0-1 patient experiences a protocol-defined DLT (refer to [Section 5.2](#)) after completion of the 4-week DLT window, an additional 3 patients will be enrolled. Once all 6 patients have completed the 4-week DLT window, the Toxicity Evaluation Committee will again assess all adverse events. If, at any time, 2 or more patients experience a protocol-defined DLT, further enrollment into the trial will be suspended.

If the treatment combination of the experimental arm demonstrates an acceptable safety profile in the Safety Run-In (one or fewer patient experiences a protocol-defined DLT), randomized enrollment into the trial will begin.

Patients will be randomly assigned to either the control arm (atezolizumab monotherapy) or experimental arm (atezolizumab + CYT107) of the trial.

The first 6 subjects enrolled in the run-in phase of the study will have PK sampling done at baseline (prior to CYT107 administration), and at week 4 prior to CYT107 administration and at 2 hours, 4 hours and 6 hours after the fourth CYT107 administration.

Anti-drug antibody testing (ADA testing) will be done on all subjects who receive CYT107. Testing will be done at baseline (prior to CYT107 administration) and at week 8, (1 month after

the last CYT107 administration.) Any subject who develops binding antibodies will be further tested for the presence of anti-CYT107 neutralizing antibodies.

Randomization in the OPEN system may be performed up to 5 business days before initiation of study treatment to allow for clinical site logistics.

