2.7 Special Studies

2.7.1 Assessment of Immunogenicity and Pharmacokinetics

The known and predicted activities of these two immunotherapeutic agents in enhancing immune responses may, in combination, influence pharmacokinetics and immunogenicity. In particular CYT107 is pharmacologically targeting lymphocytes and subject to a PK target mediated clearance (like many other blood growth factors). This is the case for G-CSF and other factors. We have validated methods to measure CYT107 blood samples for PK analysis as well as to detect and measure the presence of binding and neutralizing antibodies. We will thus measure CYT107 blood levels before the first and fourth administrations of CYT107, and at specified intervals after administration of CYT107. This would enable detection of any potential significant interference of the concomitant immunotherapies on CYT107 PK. Similarly, we will measure anti-CYT107 binding antibodies before any CYT107 administration and after the last CYT107 administration. Any subject presenting with binding antibodies will be further tested for the presence of anti-CYT107 neutralizing antibodies. While the number of patients will be too small to draw definitive conclusions, this might lead to a potential interference in the combination therapy deserving a further exploration.

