9.3 Special Studies

9.3.1 *Immunogenicity Testing*

The formation of anti-drug antibodies (ADA) and neutralizing anti-drug antibodies (NADA) to glyco-rhIL-7 (CYT107) will be evaluated in the Safety Run-In/Experimental Arm subjects only, on Cycle 1, Day 1 before the first CYT107 injection and on Cycle 3, Day 1. If positive on Cycle 3, Day 1, immunogenicity testing will be repeated at the end of the study.

9.3.1.1 *Collection of specimen(s)*

Blood draws will be performed by venipuncture on study subjects before, during and at end of treatment.

9.3.1.2 *Handling of specimen(s)*

Plasma will be isolated by the local laboratory and frozen at -80C.

9.3.1.3 *Shipping of Specimen(s)*

Plasma samples will be batch shipped overnight on dry ice to the CIML (Seattle, WA). Sites will utilize a web-based specimen system (BSI-Web) to communicate with the CIML. The CIML will coordinate the shipment of samples to the agreed upon collaborator or vendor.

9.3.1.4 *Site(s) Performing Immunogenicity Testing*

ADA and NADA to glyco-rhIL-7 (CYT107) will be performed by Eurofins Scientific (Vergeze, France) who will perform both ELISA Binding (non-neutralizing) and neutralizing antibody assays according to their Standard Operating Procedure.

9.3.2 *CYT107 Pharmacokinetics*

The pharmacokinetic profile of CYT107 levels will be assessed to determine if Atezolizumab has an effect on CYT107 PK levels. The samples will be collected before CYT107 treatment on Cycle 1, Day 1 and again on Cycle 1, Day 22.

9.3.2.1 *Collection of specimen(s)*

Blood draws will be performed by venipuncture on study subjects before and during study treatment.

Table 9.3.2 Pharmacokinetics timepoints

Cohort	Pharmacokinetic timepoints for CYT107
Safety Run-in subjects	Day 1, Immediate Pre-dose CYT107
Safety Run-in subjects	Day 1, 2 hours (\pm 15 mins) after CYT107 administration is complete
Safety Run-in subjects	Day 1, 4 hours (\pm 15 mins) after CYT107 administration is complete
Safety Run-in subjects	Day 1, 6 hours (\pm 15 mins) after CYT107 administration is complete
Safety Run-in subjects	Day 22, Immediate Pre-dose CYT107 and Atezolizumab
Safety Run-in subjects	Day 22, 2 hours (\pm 15 mins) after CYT107 administration is complete*
Safety Run-in subjects	Day 22, 4 hours (\pm 15 mins) after CYT107 administration is complete*
Safety Run-in subjects	Day 22, 6 hours (\pm 15 mins) after CYT107 administration is complete*

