j: Post-treatment tumor biopsy will be obtained prior to dosing on Cycle 4, Day 1 *or* at the End of Treatment visit, whichever occurs first.

k: Patients with known CNS metastases must also have a brain MRI imaging at all standard radiologic evaluation timepoints

l: PK (Pharmacokinetics) for CYT107 samples to be drawn on the first 6 patients enrolled in the run-in phase of the study, before the first and fourth administration and at 2hrs, 4 hrs, and 6 hrs after the first and fourth CYT107 administrations

m: Immunogenicity testing (anti-drug antibody testing or ADA testing) will be done on all subjects who receive CYT107. Testing will be done on Cycle 1, Day 1 and on Cycle 3, Day 1. If positive on Cycle 3, Day 1, testing to be repeated at End of Treatment visit.

Baseline evaluations are to be conducted within 14 days before the initiation of study treatment. Scans and x-rays must be done <4 weeks (28 days) before the initiation of study treatment. In the event that the patient's condition is deteriorating, laboratory evaluations should be repeated within 48 hours before the initiation of the next cycle of therapy. Patients receiving atezolizumab will be assessed for pulmonary signs and symptoms throughout the study.

CONTROL ARM																		
Treatment Cycle	Screening visit	Cycle 1			Cycle 2			Cycle 3			Subsequent Cycle (Repeat up to 2 year)			End of Tx	Post-Treatment Follow-up			
		Wk1	Wk2	Wk3	Wk4	Wk5	Wk6	Wk7	Wk8	Wk9	Wk10	Wk11	Wk12		At time of D/C ± 5 days	Safety FU	Disease Assessment ^h	Survival FU
Scheduling Window	Within 14 days	Day 1 ± 2	Day 8 ± 2	Day 15 ± 2	Day 1 ± 2	Day 8 ± 2	Day 15 ± 2	Day 1 ± 2	Day 8 ± 2	Day 15 ± 2	Day 1 ± 2	Day 8 ± 2	Day 15 ± 2		30 days ± 5 post DC	Every 12 ± 1 weeks	Every 12 ± 1 weeks	
Atezolizumab		A			A			A			A							
Administrative procedures																		
Informed consent	X																	
Demographics	X																	
Medical history	X																	
Concurrent meds	X	X-									X			X	X	X	X	X
Clinical Procedures/Assessments																		
Physical exam	X				X			X			X			X	X			
Vital signs ^a	X	X	X	X	X			X			X			X	X			
Height	X																	
Weight	X	X	X	X	X			X			X			X	X			
Adverse event evaluation		X-									X			X	X	X		
Immune-related AEs evaluation		X-									X			X	X	X		
Performance status	X	X	X	X	X			X			X			X	X			
EKG (as indicated)	X																	
Laboratory Assessments (Safety Labs)																		
CBC w/diff, plts	X	X	X	X	X			X			X			X	X			
Serum chemistry ^b	X	X	X	X	X			X			X			X	X			

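### The CYT107 PK sampling schedule contradicts itself, and even the full schedule cannot separate an atezolizumab effect from that of earlier CYT107 doses

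*Combined protocol and SAP*

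**What the plan says.** **Sampling.** Section 5 (Treatment Plan) has the first six run-in patients sampled before the first CYT107 dose and then "at week 4 prior to CYT107 administration and at 2 hours, 4 hours and 6 hours after the fourth CYT107 administration". Footnote l to the Section 10 calendar asks for samples "before the first and fourth administration and at 2hrs, 4 hrs, and 6 hrs after the first and fourth CYT107 administrations". Table 9.3.2 agrees with the footnote. The opening paragraph of Section 9.3.2 mentions only a collection before treatment on Day 1 and another on Day 22, with no post-dose times.

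**Day 22.** One row of Table 9.3.2 reads "Day 22, Immediate Pre-dose CYT107 and Atezolizumab", and the note under the table distinguishes the end of the CYT107 injection from the end of an atezolizumab infusion. Sections 5.1 and 5.1.1 schedule atezolizumab on Day 8 of the 28-day Cycle 1 and then on Day 1 of Cycle 2.

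**Aim.** Section 9.3.2 says the profile is taken "to determine if Atezolizumab has an effect on CYT107 PK levels". Section 2.7.1 says the sampling would allow any significant interference with CYT107 PK to be detected. It also concedes that the numbers are too small for firm conclusions. Section 1.3 lists the question as exploratory.

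**Pharmacology.** Section 2.7.1 calls CYT107 "subject to a PK target mediated clearance". Section 2.2.2.3 says that three or four weekly doses can double peripheral T cells, and that a larger T-cell pool is presumed to clear more of the drug.

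**The concern.** There are two separate problems. The first is a contradiction about which samples to draw. Without draws after the first dose there is no exposure measurement before atezolizumab, so nothing to set the fourth-dose profile against. Only six patients are sampled, and each has one Day 1.

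The second remains after the first is repaired. The only comparison available is Day 22 against Day 1 within patients who all receive both agents. Between those days they receive atezolizumab and also three CYT107 doses, and the protocol itself gives a reason why repeated CYT107 could alter its own clearance. At stake is the reading of an exploratory result: a change in exposure could be reported as a drug interaction when CYT107 alone produced it, or a real interaction could be masked.

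**Working it through.** The plan gives no sample size, test or effect size for this sub-study, and Section 13 has no PK analysis, so there is no stated figure to reproduce.

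**1. Sample counts per patient**

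| Source | Around dose 1 | Around dose 4 | Total |
|---|---|---|---|
| Section 5 | 1 (pre-dose) | 4 (pre-dose, 2, 4, 6 h) | 5 |
| Table 9.3.2 and footnote l | 4 (pre-dose, 2, 4, 6 h) | 4 (pre-dose, 2, 4, 6 h) | 8 |

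The difference is 8 − 5 = 3 per patient, or 6 × 3 = 18 of 6 × 8 = 48 over six patients, if every site followed Section 5. Time points matched between the two doses fall from 4 to 1, and the one left is pre-dose. No dose-1 exposure, and so no dose-4/dose-1 ratio, can be formed.

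**2. Day 22 and the atezolizumab schedule**

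Cycle 1 lasts 28 days, so Cycle 2 Day 1 is study day 29. Atezolizumab falls on days 8 and 29. Day 22 is 22 − 8 = 14 days after the first infusion and 29 − 22 = 7 days before the second. Patients have been exposed to atezolizumab by Day 22, but none is scheduled that day.

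**3. Can the two effects be separated?**

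Write log exposure = a + b·A + c·C, where A = 1 once atezolizumab has been given and C = 1 once three CYT107 doses have been given.

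- Day 1: (intercept, A, C) = (1, 0, 0)
- Day 22: (1, 1, 1)

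Every sampled patient contributes these same two rows. The design matrix has rank 2 for three parameters, so only the sum b + c can be estimated. More patients on this schedule, or more time points per day, leave the rank at 2. Adding repeat-dose profiles without atezolizumab, row (1, 0, 1), raises it to 3.

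**4. How large might the CYT107-only part be?**

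The documents give no figure at 10 mcg/kg. As an illustration, suppose a share f of clearance is target-mediated and scales with the T-cell pool, and the pool grows k-fold. With no atezolizumab effect:

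exposure ratio (dose 4/dose 1) = 1 / (1 + f(k − 1))

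With k = 2, the doubling in Section 2.2.2.3:

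- f = 0.10: 1/1.10 = 0.91
- f = 0.25: 1/1.25 = 0.80
- f = 0.50: 1/1.50 = 0.67
- f = 1.00: 1/2.00 = 0.50

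With k = 1.5 the range from f = 0.10 to 1.00 is 0.95 to 0.67. Both f and the linear scaling are assumptions. The formula also describes total exposure, whereas sampling stops at 6 hours.

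**5. Small numbers are a different limit**

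For a paired t-test with n = 6, two-sided 0.05 and 80% power, the detectable standardised difference is 1.43. The SD of the log difference is √2 × √ln(1 + CV²). With an assumed within-patient CV of 30% this is 1.414 × 0.294 = 0.415, so the smallest detectable fall is a ratio of exp(−1.43 × 0.415) = 0.55. For CVs of 20%, 40% and 60% it is 0.67, 0.46 and 0.32. A larger n would improve these values but would not touch step 3.

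**The case against.** The strongest reply is that the first-dose samples are planned. The sub-study's own table and the calendar footnote both list them, Section 2.7.1 provides for post-dose intervals, and Section 9 sends sites to the Laboratory Manual for the tubes at each visit. A reader might infer from Section 5 that the trial has no first-dose profile. The documents do not support that: Section 5 is out of step with the rest, and 18 of 48 is the worst case. Nor would a loss be beyond repair, since the randomized experimental arm receives the same CYT107 regimen and could be sampled by amendment.

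A reader might also infer that exposure should roughly halve by dose 4. That is not documented. The nonlinearity in Section 2.2.2.3 was seen above 20 mcg/kg/week in lymphopenic patients and above 30 in others, target-mediated disposition is only presumed to explain it, and this trial gives 10 mcg/kg. Section 2.2.2.2 also describes down-regulation and later re-expression of the IL-7 receptor, so binding capacity per cell need not stay constant. A fall is plausible, not established.

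Finally, no passage commits the team to a Day 22 versus Day 1 test or to blaming atezolizumab, the objective is exploratory, and Section 2.7.1 disclaims firm conclusions. All of that stands and limits the consequence. But the disclaimer rests on small numbers alone, while the stated aim and the detection claim still promise what this design cannot deliver at any sample size.

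**Conclusion.** The point holds in two parts, at low severity.

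First, Section 5 and the opening paragraph of 9.3.2 conflict with Table 9.3.2 and footnote l over the first-dose draws (5 versus 8 samples per patient), and the Day 22 atezolizumab reference conflicts with the dosing schedule. These are inconsistencies to reconcile, not a missing element of the plan.

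Second, under either schedule an atezolizumab effect is fully confounded with that of three earlier CYT107 doses. This needs no assumption about size or direction; it follows from every PK patient receiving both agents on one timetable. The 0.91 to 0.50 range only shows that the CYT107-only part need not be negligible, and it rests on an assumed target-mediated share of 10% to 100%, linear scaling and a doubling of T cells. A change could be misread as an interaction; the documents do not show that it would be. No primary or secondary endpoint, sample size or decision rule depends on this sub-study.

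**What to change.** - Make Section 5, the opening of 9.3.2, Table 9.3.2 and footnote l state one schedule, with the first-dose and fourth-dose profiles both specified.
- Reconcile the Day 22 atezolizumab wording in Table 9.3.2 and its note with Sections 5.1 and 5.1.1.
- Restate the aim in 9.3.2 and the detection claim in 2.7.1 as describing CYT107 exposure at doses 1 and 4.
- Report each patient's dose-4/dose-1 ratio beside the CD4+ and CD8+ counts already drawn during Cycle 1, and state that a within-patient change will not be attributed to atezolizumab.
- Compare with repeat-dose data from CYT107 given without atezolizumab only if such data exist, and note any difference in population. The documents do not show that they do. The PK studies in Section 2.2.2.3 were in patients with HIV, and the prostate cancer trial described there uses the same dose weekly for four doses but is not said to include PK sampling.

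The cost is an amendment to wording and a short descriptive summary. No samples are needed beyond those in Table 9.3.2.

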5.1 Agent Administration

Reported adverse events and potential risks are described in [Section 7](#). Appropriate dose modifications are described in [Section 6](#). No investigational or commercial agents or therapies other than those described below may be administered with the intent to treat the patient's malignancy.

Regimen Description					
EXPERIMENTAL ARM					
Agent	Premedications; Precautions	Dose	Route	Schedule	Cycle Length
Atezolizumab	antihistamines or antipyretics/ analgesics ¹	1200 mg	IV	Day 8 of Cycle 1 (28-day cycle) and Day 1 of Cycle 2+ (21-day cycles)	Cycle 1: 28 days Cycle 2+: 21 days
IL-7 (CYT107)²	None	10 mcg/kg	IM	Days 1, 8, 15 and 22 of Cycle 1 only	
CONTROL ARM					
Atezolizumab	antihistamines or antipyretics/ analgesics ¹	1200 mg	IV	Day 1 of each cycle	21 days

Note: ¹Premedication *not* permitted for the first dose on either arm; ²Calculate the required dose amount (10 mcg/kg) based on patient's baseline weight. The dose amount should be recalculated if the patient's weight changes by more than 10% from the baseline weight measurement.

5.1.1 *Atezolizumab*

All patients enrolled into this study will receive atezolizumab. Atezolizumab will be administered on Day 1 of each 21-day cycle in the control arm. Atezolizumab will be administered on Day 8 of Cycle 1 (28-day cycle) and on Day 1 of each subsequent cycle (21-day cycle) on the experimental arm. Atezolizumab may be administered up to 2 days before or after the scheduled administration date of each cycle due to administrative reasons.

Administration of atezolizumab will be performed in a setting with emergency medical facilities and staff who are trained to monitor for and respond to medical emergencies.

Atezolizumab will be administered following the CYT107 injection on Day 8 of Cycle 1 for patients enrolled in the Safety Run-in Phase and experimental arm.

For anaphylaxis precautions, see the management guidelines below. Atezolizumab infusions will be administered per the instructions outlined in the Table below.

First Infusion	Subsequent Infusions

• No premedication is permitted prior to the atezolizumab infusion.• Vital signs (pulse rate, respiratory rate, blood pressure, and temperature) should be measured within 60 minutes prior to the infusion.• Atezolizumab should be infused over 60 (± 15) minutes.• If clinically indicated, vital signs should be measured every 15 (± 5) minutes during the infusion and at 30 (± 10) minutes after the infusion.• Patients should be informed about the possibility of delayed post-infusion symptoms and instructed to contact their study physician if they develop such symptoms.	
• If the patient experienced an infusion-related reaction with any previous infusion, premedication with antihistamines, antipyretics, and/or analgesics may be administered for subsequent doses at the discretion of the investigator.• Vital signs should be measured within 60 minutes prior to the infusion.• Atezolizumab should be infused over 30 (± 10) minutes if the previous infusion was tolerated without an infusion-related reaction, or 60 (± 15) minutes if the patient experienced an infusion-related reaction with the previous infusion.• If the patient experienced an infusion-related reaction with the previous infusion or if clinically indicated, vital signs should be measured during the infusion and at 30 (± 10) minutes after the infusion.

For anaphylaxis precautions, use the following procedure:

Equipment Needed

- Monitoring devices: ECG monitor, blood pressure monitor, oxygen saturation monitor, and thermometer
- Oxygen
- Epinephrine for subcutaneous, IV, intramuscular, and/or endotracheal use in accordance with standard practice
- Antihistamines
- Corticosteroids
- Intravenous infusion solutions, tubing, catheters, and tape

Procedures

In the event of a suspected anaphylactic reaction during atezolizumab infusion, the following procedures should be performed:

- Stop the study drug infusion.
- Call for additional medical assistance.
- Maintain an adequate airway.
- Ensure that appropriate monitoring is in place, with continuous ECG and pulse oximetry monitoring, if possible.

- Administer antihistamines, epinephrine, or other medications as required by patient status and directed by the physician in charge.
- Continue to observe the patient and document observation.

All patients randomly assigned to the experimental treatment arm in Part 2 will also receive CYT107 in addition to atezolizumab.

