5.1.2 Recombinant Human IL-7 (CYT107)

Patients enrolled in the Safety Run-in phase and patients randomly assigned to the experimental arm of the trial will receive recombinant human IL-7 (CYT107). The patients will receive 10 mcg/kg of IL-7 (CYT107) IM on days 1, 8, 15 and 22 of Cycle 1 only. The CYT107 dose must be administered before atezolizumab on Day 8 of Cycle 1.

For patient with a Body Mass Index (BMI) >30, an adjusted body weight will be used to calculate the final dose the patient will receive. Please refer to [Appendix D](#) for details on the adjusted body weight calculation.

Patients receiving CYT107 will have their vital signs (heart rate, respiratory rate, blood pressure, and temperature) determined within 60 minutes before the first CYT107 injection on day 1, and 2 hours (\pm 15 minutes) after the injection.

On day 8, vital signs will be monitored as described above ([Section 5.1.1](#)) following the guidelines for the first atezolizumab infusion.

On days 15 and 22, vital signs will be determined within 60 minutes before and within 30 minutes after the injection.

Patients will be informed about the possibility of the development of an allergic reaction to CYT107 (hives, bronchospasm, rash, etc.) and instructed to contact their study physician if they develop such symptoms.

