CYT107 is provided to the NCI under a Collaborative Agreement between the Pharmaceutical Collaborator and the DCTD, NCI (see [Section 12.4](#)).

Preparation: Do not shake vials. Remove number of vials required for dose preparation from the freezer and thaw at refrigerated temperature (2-8°C) for 1 hour prior to dose preparation. Once thawed, inspect vials for any visible particulate matter. If observed, discard vials. Aseptically withdraw the required dose volume into a syringe for administration.

Storage: Store vials in their original box frozen at -20°C.

If a storage temperature excursion is identified, promptly return CYT107 vials to -20°C freezer and quarantine the supplies. Provide a detailed report of the excursion (including documentation of temperature monitoring and duration of the excursion) to [contact] for determination of suitability.

Stability: Stability studies of the intact vials are ongoing. Do not re-freeze thawed vials. Intact vials may be removed from the freezer and kept at refrigerated temperature for a maximum of 12 hours prior to dose administration. Once dose is withdrawn into a syringe, administer immediately. If necessary, prepared syringes may be stored refrigerated for up to 6 hours prior to administration. Vials are for single-use only. Destroy any remaining contents following dose preparation.

Route and Method of Administration: Intramuscular (IM) injection. Inject slowly (over 10-20 seconds) into Deltoid muscle or muscle of the thighs or buttocks, away from joints, nerves or bones. Rotate injection sites with each injection.

Potential Drug Interactions: *In-vitro*, CYT107 did not inhibit isoenzymes CYP1A2, CYP2A6, CYP2B6, CYP2C8, CYP2C9, CYP2C19, CYP2D6, CYP2E1 and CYP3A4. *In vitro*, CYT107 did not induce isoenzymes CYP1A, CYP2B6 and CYP3A4. At concentrations tested, it is unlikely CYT107 will cause drug-drug interactions.

Patient Care Implications: Advise study participants to use effective contraception while receiving study treatment and for at least 2 months after the last dose.

For patient with a Body Mass Index (BMI) >30, an adjusted body weight will be used to calculate the final dose to be administered. Please refer to [Appendix D](#) for details on the adjusted body weight calculation.

8.1.3 *Agent Ordering and Agent Accountability*

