APPENDIX D DOSE ADJUSTMENT FOR OBESE PATIENT

Obesity is defined as a BMI >30 (NHLBI Class 1 Obesity)

In order to determine the proper dose for patients classified as obese, an adjusted body weight is calculated. The following steps are provided to assist with the process:

BMI Chart

BMI	19	20	21	22	23	24	25	26	27	28	29	30	35	40
Ht	Wt (lbs)													
4'10"	91	96	100	105	110	115	119	124	129	134	138	143	167	191
4'11"	94	99	104	109	114	119	124	128	133	138	143	148	173	198
5'0"	97	102	107	112	118	123	128	133	138	143	148	153	179	204
5'1"	100	106	111	116	122	127	132	137	143	148	153	158	185	211
5'2"	104	109	115	120	126	131	136	142	147	153	158	164	191	218
5'3"	107	113	118	124	130	135	141	146	152	158	163	169	197	225
5'4"	110	116	122	128	134	140	145	151	157	163	169	174	204	232
5'5"	114	120	126	132	138	144	150	156	162	168	174	180	210	240
5'6"	118	124	130	136	142	148	155	161	167	173	179	186	216	247
5'7"	121	127	134	140	146	153	159	166	172	178	185	191	223	255
5'8"	125	131	138	144	151	158	164	171	177	184	190	197	230	262
5'9"	128	135	142	149	155	162	169	176	182	189	196	203	236	270
5'10"	132	139	146	153	160	167	174	181	188	195	202	207	243	278
5'11"	136	143	150	157	165	172	179	186	193	200	208	215	250	286
6'0"	140	147	154	162	169	177	184	191	199	206	213	221	258	294
6'1"	144	151	159	166	174	182	189	197	204	212	219	227	265	302
6'2"	148	155	163	171	179	186	194	202	210	218	225	233	272	311
6'3"	152	160	168	176	184	192	200	208	216	224	232	240	279	319
6.4"	156	164	172	180	189	197	205	213	221	230	238	246	287	328

If BMI >30, proceed with the following steps:

- **Determine Ideal Weight (1 kg = 2.2 lbs)**

Males: $50 \text{ kg} + (2.3 \text{ kg/inch over 5 feet})$

Females: $45.5 \text{ kg} + (2.3 \text{ kg/inch over 5 feet})$
(Patients less than 5 feet: subtract 2.3 kg/inch)

- **Determine Adjusted Body Weight:**

$\text{Ideal Weight} + 0.25 (\text{actual weight} - \text{ideal weight}) = \text{Adjusted Body Weight}$

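### CYT107 dosing weight: the Appendix D chart misprints the BMI-30 weight at 5 ft 10 in, and note 2 of the regimen table is not reconciled with the adjusted-weight rule

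*Combined protocol and SAP*

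**What the plan says.** The dosing weight for CYT107 appears in four places.

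- **Section 5.1, regimen table, note 2.** The 10 mcg/kg amount is "based on patient's baseline weight. The dose amount should be recalculated if the patient's weight changes by more than 10% from the baseline weight measurement". BMI and Appendix D are not mentioned.
- **Section 5.1.2.** "The patients will receive 10 mcg/kg of IL-7 (CYT107) IM on days 1, 8, 15 and 22 of Cycle 1 only". For BMI above 30, "an adjusted body weight will be used to calculate the final dose the patient will receive", with a reference to Appendix D.
- **Section 8.1.2 (pharmaceutical information).** For BMI above 30, "an adjusted body weight will be used to calculate the final dose to be administered".
- **Appendix D.** "In order to determine the proper dose for patients classified as obese, an adjusted body weight is calculated". The cut-off is a BMI strictly above 30. A chart of weight by height and BMI comes first, followed by formulas for ideal and adjusted weight.

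In the chart, the row for 5 ft 10 in reads "132 139 146 153 160 167 174 181 188 195 202 207 243 278". The columns are BMI 19 to 30 in single units, then 35 and 40, so the BMI-30 entry is 207 lb.

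**The concern.** CYT107 is the agent that separates the randomized arms. The plan has about 30 patients receiving it (6 in the run-in and 24 of the 48 randomized) at about 8 sites. The regimen table is a natural first place for a site to look for the dose, and its note does not point to the adjusted-weight rule. A site that works from the table and a site that works from section 5.1.2 could give materially different amounts to the same patient with BMI above 30.

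The chart raises a separate question. Its BMI-30 column is where the dosing weight changes from actual to adjusted, so an entry that is too low in that column moves the threshold for that height. The 5 ft 10 in row rises by 7 lb per BMI unit up to 202 lb at BMI 29, then by only 5 lb to 207.

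**Working it through.** **Inputs.** All come from the protocol except the BMI formula.

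- Dose: 10 mcg/kg (sections 5.1 and 5.1.2).
- Conversion: 1 kg = 2.2 lb (Appendix D).
- Ideal weight (IBW): men 50 kg, women 45.5 kg, plus 2.3 kg per inch over 5 ft, or minus 2.3 kg per inch under (Appendix D).
- Adjusted weight: IBW + 0.25 × (actual − IBW) (Appendix D).
- BMI = 703.07 × lb / in². The protocol does not print this. It is assumed as the standard definition, and the rest of the chart fits it.

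**1. The chart cell**

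Printed figure: 207 lb for BMI 30 at 70 inches.

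- Weight at BMI 30: 30 × 70² / 703.07 = 209.1 lb.
- BMI at 207 lb: 703.07 × 207 / 4900 = 29.70.

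All 266 cells were recomputed. This one is 2.1 lb low. No other cell is off by more than about 1.2 lb, and the other 18 entries in the BMI-30 column are within 0.8 lb.

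The chart also shows the error without the outside formula. Scaling the same row gives 243 × 30/35 = 208.3 lb and 278 × 30/40 = 208.5 lb. Down the BMI-30 column, the entries for 5 ft 9 in, 5 ft 10 in and 5 ft 11 in are 203, 207 and 215: steps of 4 and 8, where about 6 and 6 would be expected.

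**2. What the cell changes**

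At 5 ft 10 in, 208 lb is BMI 29.84 and 209 lb is BMI 29.99. Neither exceeds 30, but both exceed the printed 207 lb. IBW at this height is 73.0 kg (man) or 68.5 kg (woman).

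| Weight | kg | Dose on actual weight | Man, adjusted | Woman, adjusted |
|---|---|---|---|---|
| 208 lb | 94.55 | 945 mcg | 784 mcg (−17.1%) | 750 mcg (−20.7%) |
| 209 lb | 95.00 | 950 mcg | 785 mcg (−17.4%) | 751 mcg (−20.9%) |

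Worked case, man at 208 lb: 73 + 0.25 × (94.55 − 73) = 78.39 kg, so 784 mcg.

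**3. Note 2 alone against the adjusted-weight rule**

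The relative difference is 0.75 × (1 − IBW / actual weight). At BMI 30, over the chart's heights (4 ft 10 in to 6 ft 4 in):

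- men: 22.7% at the shortest height to 16.8% at the tallest;
- women: 27.9% to 19.8%.

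Check, man at 5 ft 10 in: 0.75 × (1 − 73.0/94.8) = 17.3%.

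Above BMI 30 the gap widens:

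| Patient | BMI | Note 2 alone | Adjusted weight | Difference |
|---|---|---|---|---|
| Man, 5 ft 10 in | 35 | 1106 mcg | 824 mcg | about −25% |
| Man, 5 ft 10 in | 40 | 1265 mcg | 864 mcg | −32% |
| Woman, 5 ft 4 in | 35 | 925 mcg | 641 mcg | −31% |
| Woman, 5 ft 4 in | 40 | 1057 mcg | 675 mcg | −36% |

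**4. Recalculation after a change of more than 10%**

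Take a 98 kg man of 5 ft 10 in (BMI 31.0). Adjusted weight is 73 + 0.25 × 25 = 79.25 kg, so about 793 mcg. If he loses 10.1%, he weighs 88.1 kg.

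- BMI re-checked, now below 30: actual weight applies, 881 mcg.
- BMI not re-checked: 73 + 0.25 × 15.1 = 76.8 kg, so 768 mcg.

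The protocol does not say which calculation is meant.

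**The case against.** The strongest reply is that this is a general rule with a specific exception. Section 5.1.2 is part of section 5.1, it states the BMI >30 rule and it links to Appendix D. The pharmacy text in 8.1.2 repeats it. To dose on actual weight above BMI 30, a site would have to overlook three places. That reading is reasonable, so this is a missing cross-reference and not a flat contradiction. It does not settle recalculation, because only note 2 mentions that.

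On the trigger, the reply is right: note 2 ties the 10% to the baseline weight measurement, which points to measured weight. What remains open is the weight used for the new dose and whether BMI is re-checked. A loss above 10% is also unlikely within the three weeks from day 1 to day 22, so the example above shows the gap and not an expected case.

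On the chart, the governing criterion is BMI, height and weight are both collected at screening, and a site can compute BMI directly. The cell affects one height, a band of about 2 lb, and only a site that relies on the chart. A copying or text-extraction error could also explain it. All of this limits the effect. It does not make 207 lb consistent with BMI 30.

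A reader might infer three stronger points that the documents do not support:

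- **That the cell or the wording causes the drop in dose at BMI 30.** It comes from applying adjusted weight only above a sharp threshold, and it would remain with a corrected chart and uniform wording.
- **That adjusted dosing falls below an effective range.** Section 2.2.2.3 cites 10 to 20 mcg/kg as able to double T cells, but it does not say whether those doses used actual or adjusted weight in obese patients.
- **That non-obese patients will in fact be misclassified.** Nothing shows that any patient falls in the band or that any site uses the chart alone.

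**Conclusion.** Two defects in operative dosing instructions stand.

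First, the BMI-30 entry at 5 ft 10 in is about 2 lb too low. Used alone, the chart would put a patient of 208 or 209 lb on adjusted weight, with about 17% (man) to 21% (woman) less CYT107 than the protocol's own BMI >30 rule gives. This rests on the standard BMI definition and on the source chart also reading 207.

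Second, note 2 gives the dosing weight without the exception stated in 5.1.2, 8.1.2 and Appendix D. Followed alone, it differs from the adjusted-weight rule by about 17% to 28% just above BMI 30 and by up to 36% in the BMI-40 examples. The weight basis for recalculation is not stated.

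The step at BMI 30 is a consequence of the stated rule and is not counted as an error. The sample size and power in section 13.3 do not depend on this point. No view is taken on which dosing weight or threshold is right.

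**What to change.** 1. Check the 5 ft 10 in, BMI-30 cell in Appendix D against its source. If the source also reads 207, correct the cell, or replace the chart lookup with the BMI formula.
2. Reconcile note 2 of the regimen table with sections 5.1.2 and 8.1.2 and Appendix D, so that all four places give one instruction on dosing weight.
3. State, for recalculation after a weight change of more than 10%, whether BMI is re-checked and which weight is used. The choice is the sponsor's.

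The cost is one chart cell and a few lines of protocol wording. No new data, analysis or sample-size change is needed.
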